12.6.3. Propensity Score Analysis

In addition to the analyses of the primary effectiveness and safety endpoints noted above, a propensity analysis will be conducted to address the effect of potential confounding variables on study conclusions. Risk factors that will be analyzed include, but are not limited to:

- Age
- Parity
- BMI
- Smoking status
- Diabetes
- Hysterectomy status
- History of Multiple Urinary Tract Infections

For this analysis, a logistic regression model will be used to calculate the probability of treatment assignment given the covariates listed above (i.e., the propensity score). The covariates will not be grouped, resulting in one propensity score for each subject. The propensity score will be used in an adjusted regression model for each primary endpoint. A logistic regression model will be used for the primary effectiveness and safety endpoints.

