7.8 Propensity Analysis

In addition to the primary and secondary analyses of the effectiveness and safety endpoints, a propensity analysis will be conducted to address the effect of potential confounding variables on our conclusion. Risk factors that will be analyzed are outlined in Section 3.3.5.

For this analysis, a logistic regression model will be used to calculate the probability of treatment assignment given the covariates listed above (i.e., the propensity score). The covariates will not be grouped, resulting in one propensity score for each subject. The propensity score will be used in an adjusted regression model for each primary endpoint. A logistic regression model will be used for the primary effectiveness and safety endpoints.

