12.4. Demographics and Baseline Characteristics

Demographics and baseline characteristics of the ITT analysis population will be summarized. These factors will include (but not be limited to):

- Age
- Ethnicity

- Race
- BMI
- Medical history (including diagnosis of SUI)
- Parity
- Smoking status
- Diabetes
- Hysterectomy status
- History of Multiple UTIs

In order to assess if the Altis and Comparator study populations are similar, demographics and baseline characteristics will be compared by t-tests for continuous factors and chi square tests for categorical factors, or non-parametric tests as appropriate. A propensity score analysis will also be performed. If significant differences are found between groups, the impact of relevant factor(s) on success rates will be assessed.

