The primary analysis of this endpoint will include all available data and ‘presumed failures’ from the mITT analysis population. Presumed failures are defined as subjects with missing data where it is known that the cause of the data loss is either related (1) to an adverse event, including death, or (2) to a device failure. ‘Presumed failures’ will be considered failures for all primary effectiveness endpoint analyses. ‘Presumed failures’ will contribute available data up to the point of failure, and will be considered failures in the primary effectiveness endpoint analysis after the point of failure. Subjects with missing data for other reasons will be ignored in the primary analysis. As described above, the primary effectiveness endpoint will also be summarized for the PP analysis set, following the same logic as the main analysis in the mITT analysis set.

Sensitivity Analyses

The following sensitivity analyses will be performed on the primary effectiveness endpoint:

- An analysis utilizing multiple imputation (MI) for missing values will be performed for the primary effectiveness endpoint based on the mITT analysis population. Selection of variables for the MI analysis will be performed by first assessing the correlation of relevant baseline variables including, but not limited to: baseline age, investigational site, and baseline pad weight. The initial list of candidate variables may be adjusted to allow for proper model convergence. A total of 100 imputed datasets will be created to determine the imputed effect size.
- The primary effectiveness endpoint will also be assessed in the ITT analysis population. Again, multiple imputation method will be employed to impute missing values.
 - A comparison of relevant baseline and clinical variables between missing and non-missing subjects will also be used to assess the likelihood that missingness is differential or non-differential. Non-differential missingness with respect to the outcome is known to not bias results, but to attenuate a

given effect size. Should missing subjects and non-missing subjects demonstrate high concordance on baseline factors, it can be reasonably argued that missingness is non-differential and therefore results from complete case analyses are unbiased.

- Additional sensitivity analyses for the primary effectiveness endpoint will include best case, worst case and tipping point analysis, and will be based on the mITT analysis set.

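### Crude risk differences decide both primary endpoints in this non-randomised cohort, and the planned propensity-adjusted logistic model is not put on the margins' scale

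*SAP*

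**What the plan says.** Protocol 5.5 and SAP 8.1 state that there is no randomisation. SAP section 7 (Trial Success Criteria) makes success depend on meeting both primary objectives. SAP 12.6.1 and 12.6.2 decide each objective with a Z-test and 95% CI for Comparator minus Altis, without covariates. The upper limit must lie below 0.15 for effectiveness, and the lower limit above -0.10 for safety. The same intervals, compared with 0, permit a superiority claim.

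Confounding is dealt with in two places.

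- SAP 12.6.3, matching Protocol 7.8, says that "a propensity analysis will be conducted to address the effect of potential confounding variables on study conclusions". It adds: "The propensity score will be used in an adjusted regression model for each primary endpoint". On the type of model it says: "A logistic regression model will be used for the primary effectiveness and safety endpoints". Seven covariates are named (age, parity, BMI, smoking, diabetes, hysterectomy, multiple urinary tract infections), introduced by "Risk factors that will be analyzed include, but are not limited to".
- SAP 12.4 compares baseline characteristics by significance tests and says: "If significant differences are found between groups, the impact of relevant factor(s) on success rates will be assessed".

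Baseline 24-hour pad weight is collected (Protocol 5.1). The multiple imputation in SAP 12.6.1 draws on "relevant baseline variables including, but not limited to: baseline age, investigational site, and baseline pad weight". Protocol 7.2 and SAP 12.10 also call for effectiveness analyses in women with baseline leakage of at least 4 g, and SAP 12.10 adds a 1.3 g cut-off.

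**The concern.** The propensity analysis is the plan's own safeguard against differences between the women who received each device. To do that job it must show whether each margin is still met after adjustment. As written, it yields a logistic model with no stated effect measure, no comparison with a margin and no account of how a conflicting result would be described. A reader of the final report could be given a crude risk difference that passes and an adjusted odds ratio that cannot be set beside it.

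The score may also omit the baseline value from which the effectiveness endpoint is calculated. If pad weight differs between groups and predicts response, a score built only from the seven named covariates would correct for it only as far as those covariates are related to it.

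At stake are two non-inferiority conclusions, and possibly superiority claims, drawn from a comparison that confounding could shift either way.

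**Working it through.** **1. The plan's sample sizes reproduce from the crude test.** Inputs (SAP 10.1, 10.2, 10.4): one-sided 0.025, 80% power, equal true rates.

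n = (1.960 + 0.842)² × 2p(1 − p) / margin²

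- Effectiveness, p = 0.75, margin 0.15: 130.8, so 131 per arm; 131/0.8 gives 164.
- Safety, p = 0.10, margin 0.10: 141.3, so 142 per arm; 142/0.8 gives 178.

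These match the documents, so the study is sized for the unadjusted risk difference.

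**2. No single odds ratio stands for a margin.** Odds ratio (Altis/Comparator) with the true difference at the margin:

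| Endpoint | Comparator rate | Odds ratio at margin |
|---|---|---|
| Safety, +0.10 | 2.7% | 5.24 |
| | 5% | 3.35 |
| | 10% | 2.25 |
| | 15% | 1.89 |
| Effectiveness, −0.15 | 70% | 0.52 |
| | 75% | 0.50 |
| | 80% | 0.46 |
| | 85% | 0.41 |

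For example, (0.20/0.80)/(0.10/0.90) = 2.25. Read the other way, an adjusted odds ratio of 2.25 is an excess of 3.2, 5.6, 10.0 or 13.4 points at comparator rates of 2.7%, 5%, 10% or 15%. Two of these rates are the plan's own: SAP 10.2 assumes 10% and cites 2.7% through 12 months in the IDE study. The 5% and 15% rates are added for range.

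**3. False non-inferiority if the crude difference is biased.** The size and direction of the bias are assumptions. The true difference is placed exactly at the margin, and each endpoint is taken alone.

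Rate = Φ(b/SE − 1.96), where b is the bias in favour of Altis and SE² = [pC(1 − pC) + pT(1 − pT)]/n

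- Effectiveness: pC = 0.75, pT = 0.60 + b, n = 142 evaluable per arm (178 × 0.8).
- Safety: pC = 0.10, pT = 0.20 − b, n = 178 per arm, because SAP 10.2 counts subjects with missing data as event-free.

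| Endpoint | Bias | SE | False non-inferiority |
|---|---|---|---|
| Effectiveness | 0 | 0.0549 | 2.5% |
| | 2 points for Altis | 0.0546 | 5.6% |
| | 4 points for Altis | 0.0542 | 11.1% |
| | 2 points against | 0.0551 | 1.0% |
| | 4 points against | 0.0553 | 0.4% |
| Safety | 0 | 0.0375 | 2.5% |
| | 2 points for Altis | 0.0365 | 7.9% |
| | 3 points for Altis | 0.0360 | 13.0% |
| | 2 points against | 0.0383 | 0.7% |
| | 3 points against | 0.0387 | 0.3% |

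For bias favouring Altis, comparator rates of 70% to 85% give 5.4–6.1% and 10.6–13.2% for effectiveness. Comparator rates of 5% to 15% give 9.8–7.0% and 17.4–11.0% for safety.

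**4. The significance trigger in SAP 12.4.** These tests run in the ITT population, which SAP 12.2 defines as everyone enrolled, so at least 178 per arm at the planned size. For one continuous factor with a standardised difference d, the test statistic has mean d × √(178/2).

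- d = 0.20: mean 1.887, p < 0.05 in about 47% of studies.
- d = 0.38: mean 3.585, p < 0.05 in about 95% of studies.

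**The case against.** The strongest reply is that the plan already addresses confounding. The propensity analysis is unconditional, covers both primary endpoints, and is described in the protocol as well as the SAP. That stands: a reader might infer that no adjustment is planned, and the documents contradict this.

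The logistic model is also usable. Its fitted probabilities can be averaged into a risk difference. Only the odds ratio by itself cannot be read against the margins, so the gap is an output that was not requested.

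On pad weight, the covariate list is open, so inclusion is permitted. The leakage subgroups restrict on this variable, although restriction above a cut-off does not adjust for imbalance within the subgroup. The endpoint is a percentage change from each woman's own baseline, and the documents do not say whether baseline weight predicts response. This part is therefore a modest one.

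The SAP 12.4 trigger would usually catch a large imbalance (about 95% at 0.38 SD), and it tests many factors. It misses a 0.20 SD imbalance in a given factor about half the time, and pad weight is not named on that list, which is also open. Whatever it flags leads only to an unspecified assessment.

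Finally, the plan attaches no formal consequence to its other sensitivity analyses either. That is fair, and it is why the remedy asks for a comparable number and plain reporting, and leaves the decision rule as it is.

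**Conclusion.** The point holds and should be fixed. In a non-randomised cohort, crude intervals alone settle both primary conclusions. The analysis meant to test those conclusions is not asked for a result that can be compared with 0.15 or -0.10. Baseline pad weight may be in the score but is not assured.

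The size depends on assumed bias. A shift of 2 to 4 points favouring Altis on effectiveness gives 5.6% to 11.1% false non-inferiority, and 2 to 3 points on safety gives 7.9% to 13.0%, against a nominal 2.5%. The same shifts against Altis give 1.0% to 0.4% and 0.7% to 0.3%. These are single-endpoint rates with the truth at the margin; study success needs both endpoints.

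A reader might infer that the crude analysis is known to favour Altis. The documents do not support that: they give neither the size nor the direction of any confounding. Nor do they require that the adjusted interval replace the crude test as primary. Both documents place the propensity analysis alongside the primary analyses.

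**What to change.** Change SAP 12.6.3 only. The SAP states that it prevails over the protocol, so no protocol edit is needed.

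1. Standardise the planned logistic model (treatment plus propensity score) over the subjects in the mITT main analysis. Report an adjusted risk difference, Comparator minus Altis, with a 95% CI for each primary endpoint. Compare it with the same margins, and with 0 for superiority. State the CI method, and choose one suited to few events for safety: 356 subjects give 35.6 expected events at 10% but only 9.6 at 2.7%.
2. Name baseline 24-hour pad weight as a covariate in the single propensity score.
3. Report the adjusted result beside the crude one. Describe a non-inferiority or superiority conclusion that the adjusted interval does not support as not robust to confounding.

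The cost is SAP wording and modest programming; the data are already collected. There is no power cost while the crude test keeps its formal role. Any formal role for the adjusted interval is the sponsor's choice, to be fixed before the final analysis. If it alone decided, power would be Φ(margin/(SE√v) − 1.96) with v the variance inflation. For an assumed v of 1.05 to 1.30, effectiveness power falls from 83% to 81–73% (142 per arm, SE 0.0514) and safety power from 88% to 87–79% (178 per arm, SE 0.0318).

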3.2.1 General

This study is a prospective, post-market, multi-center, cohort assessment comparing Altis SIS (Study Subjects) and transobturator and/or retropubic slings (Control Subjects) in the treatment of stress urinary incontinence. Subjects will be followed for 36 months, with scheduled follow-up visits at 6 months, 12 months, 18 months, 24 months, and 36 months.

[figure not shown]
The study will be analyzed under the intent-to-treat principle. A propensity score analysis will be used to address potential sources of bias due to the cohort design. Additional mechanisms to control potential sources of bias include: rigorous well-defined inclusion/exclusion criteria, utilization of screening and enrollment log, and consecutive enrollment of eligible subjects.

Treatment Group Subjects	Control Group Subjects
Altis Single Incision Sling	Transobturator or Retropubic Slings
N= 178	N= 178

Patient enrollment will continue until the required sample size is successfully reached. The study may include up to 40 U.S. and international sites. No site may attempt to implant more than 20% of subjects in each respective arm without prior approval from Coloplast Corp.

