3.3.5 Risk Factors

In addition to the primary and secondary endpoint analysis, a propensity analysis will be conducted to address potential risk factors of adverse events and procedural success. Risk factors that will be analyzed include but are not limited to:

- Age
- Parity
- BMI
- Smoking Status
- Diabetes
- Hysterectomy status
- History of Multiple Urinary Tract Infections

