This SAP should be read in conjunction with the study protocol and electronic case report forms (eCRF). This version of the plan has been developed with respect to the Altis 522 protocol version 4.0, dated November 01, 2018. Any changes to the protocol or eCRFs may necessitate updates to the SAP. If differences exist between the protocol and the SAP, the SAP shall prevail.

3. Applicable Documents

Document Number	Document Title
Study ID SU020	A Post-Market Evaluation of the Altis Single Incision Sling System versus Transobturator or Retropubic Mesh Sling in the Treatment of Female Stress Urinary Incontinence (Altis 522 Study)

4. Software

All tables, listings and figures will be produced using SAS Version 9.4 (SAS Institute, Cary, NC.) or a later version of SAS. All output will be in Microsoft Word, Microsoft Excel or RTF format. Other reporting software (such as R) may be used for data analysis, summarizations or visualization of data as necessary.

5. Trial Objectives

The purpose of this postmarket study is to compare the safety and effectiveness of the Altis Single Incision Sling (SIS) to an FDA cleared transobturator and/or retropubic mesh sling through 36 months.

The primary safety and effectiveness objectives of this study are:

1. To demonstrate that the rate of device and/or procedure related serious adverse events associated with use of Altis SIS is non-inferior compared to the rate associated with use of transobturator and/or retropubic slings at 36 months.
2. To demonstrate that the rate of effectiveness associated with use of Altis SIS is non-inferior to the rate associated with use of transobturator or retropubic mesh slings for the treatment of stress urinary incontinence at 6 months.

The secondary objectives of this study are:

3. To demonstrate that the rate of device and/or procedure related adverse events defined as organ perforation, bleeding, mesh exposure in the vagina, mesh erosion into the bladder, pelvic pain, infection, de novo dyspareunia, urinary retention, recurrent incontinence, other urinary problems and neuromuscular problems associated with use of Altis SIS is non-inferior compared to the rate associated with use of transobturator and/or retropubic slings at 36 months.
4. To demonstrate that the rate of revision/resurgery associated with use of Altis SIS is non-inferior compared to the rate associated with use of transobturator and/or retropubic slings at 36 months.

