8.1 Randomization

This is not a randomized study.

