12.7.1. Secondary Safety Analyses

Main Analysis

The number and proportion of subjects experiencing any device- and/or procedure-related adverse event will be tabulated for each group. Non-inferiority at 36 months will be calculated using a normal approximation test (Z-test) for a difference in binomial proportion. Non-inferiority will be achieved if the lower limit of the 95% confidence interval for the difference in proportions (Comparator – Altis) is greater than -0.15 in the ITT analysis population. If non-inferiority is achieved and the lower limit of the 95% confidence interval for difference in proportions (Comparator – Altis) is greater than 0, superiority of Altis can also be claimed. As this follows a simple closed test procedure, no multiplicity adjustment is necessary.

The primary analysis of this endpoint will include all available data from the mITT analysis population. Subjects that have not experienced a device- and/or procedure-related event and who have missing data at 36 months will be assumed to be free of such an adverse event.

Sensitivity Analyses

The potential impact on the endpoint inference of all subjects with missing endpoint data will be assessed via various sensitivity analyses that include best case, worst case and tipping point analysis. In addition, a Kaplan-Meier product limit analysis that right censors subjects lost to follow-up will be conducted to further understand the potential impact of subject loss. All sensitivity analyses will be based on the mITT analysis set.

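### The propensity-adjusted model is specified only for the two primary endpoints, so the two powered secondary safety claims in this non-randomised cohort rest on crude tests with no prespecified adjusted estimate

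*SAP*

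**What the plan says.** SAP 8.1 states "This is not a randomized study". Protocol 3.2.1 names the remedy for that design: "A propensity score analysis will be used to address potential sources of bias due to the cohort design". Protocol 3.3.5 lists age, parity, BMI, smoking, diabetes, hysterectomy and repeated urinary tract infections, and gives the purpose of the analysis as "to address potential risk factors of adverse events and procedural success".

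The model itself is narrower. SAP 12.6.3 says "The propensity score will be used in an adjusted regression model for each primary endpoint" and adds "A logistic regression model will be used for the primary effectiveness and safety endpoints". Protocol 7.8 opens more broadly ("In addition to the primary and secondary analyses of the effectiveness and safety endpoints, a propensity analysis will be conducted"), but the only outcome model it goes on to describe is also for the primary endpoints. The SAP's opening section settles any conflict: "If differences exist between the protocol and the SAP, the SAP shall prevail".

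SAP 12.7.1 (related adverse events, margin 0.15) and SAP 12.7.2 (revision/resurgery, margin 0.10) each use a normal-approximation test of two crude proportions. Each says that, after non-inferiority, "superiority of Altis can also be claimed" if the lower confidence limit is above zero. SAP 10.4 places both in a fixed testing order after primary safety.

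**The concern.** Protocol 3.3.5 treats the listed covariates as drivers of adverse events. If surgeons choose the sling partly on those factors, the arms will differ in underlying risk, and the crude difference will mix that with any device effect. For the primary endpoints, the reader will at least see an adjusted result beside the crude one. For the two powered secondary safety endpoints, no such result is prespecified.

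The sensitivity analyses in SAP 12.7.1 and 12.7.2 (best case, worst case, tipping point, Kaplan-Meier) deal with missing data and loss to follow-up. None deals with confounding. Two claims about device safety could therefore be made without the check that the protocol itself names as the answer to cohort bias.

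**Working it through.** **Inputs from the documents.** 178 per arm (SAP Trial Design); one-sided 0.025 (SAP 10.4); related adverse events 20% in each group, margin 0.15 (SAP 10.3, 12.7.1); revision/resurgery margin 0.10 (SAP 12.7.2). The revision rate is not stated. SAP 10.3 expects it to be below the primary safety rate, which is taken as 10%, so 5% and 10% are both shown.

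**Assumed, because the documents give no figure.** One binary risk factor with risk ratio 2, more common in the comparator arm: 33% v 27%, 35% v 25%, or 40% v 20%.

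**Step 1: the plan's own figure.** n = (1.960 + 0.842)² × 2 × 0.20 × 0.80 / 0.15² = 111.6, so 112 per group. 112/0.80 = 140, which is the attrition-adjusted number in Protocol 7.9.4. Both reproduce; no sample size is in dispute.

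**Step 2: bias.** With risk ratio 2, the comparator rate is pC = p0(1 + fC), where fC and fT are the prevalences in the comparator and Altis arms. With no device effect, the Altis rate is p0(1 + fT), so the bias is b = p0(fC − fT). For 40% v 20%: p0 = 0.20/1.40 = 0.1429; the Altis rate is 0.1429 × 1.20 = 0.1714; b = 2.9 points.

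**Step 3: error rates.** The chance of a false claim is about Φ(b/SE − 1.96).
- Superiority, no true difference, 40% v 20%: SE = √[(0.20 × 0.80 + 0.1714 × 0.8286)/178] = 0.0412, giving Φ(0.69 − 1.96) = 10.3%.
- Non-inferiority, true excess exactly 15 points, so the crude Altis rate is 0.3214: SE = √[(0.20 × 0.80 + 0.3214 × 0.6786)/178] = 0.0461, giving Φ(0.62 − 1.96) = 9.0%.

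The tables give exact binomial enumeration of the same decision rule, taking each test alone.

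Related adverse events, comparator rate 20%:

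| Prevalence, comparator v Altis | Bias (points) | False non-inferiority | False superiority |
|---|---|---|---|
| equal | 0 | 2.5% | 2.6% |
| 33% v 27% | 0.9 | 3.9% | 4.2% |
| 35% v 25% | 1.5 | 5.1% | 5.6% |
| 40% v 20% | 2.9 | 9.0% | 10.6% |

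Revision/resurgery:

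| Comparator rate | Prevalence | Bias (points) | False non-inferiority | False superiority |
|---|---|---|---|---|
| 5% | equal | 0 | 3.0% | 2.4% |
| 5% | 33% v 27% | 0.2 | 3.6% | 3.0% |
| 5% | 40% v 20% | 0.7 | 5.0% | 4.9% |
| 10% | equal | 0 | 2.7% | 2.6% |
| 10% | 33% v 27% | 0.5 | 3.6% | 3.6% |
| 10% | 40% v 20% | 1.4 | 6.2% | 7.0% |

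**Step 4: imbalance the other way.** If 40% of Altis and 20% of comparator women carry the factor, p0 = 0.20/1.20 = 0.1667 and the Altis rate is 0.1667 × 1.40 = 0.2333. SE = √[(0.20 × 0.80 + 0.2333 × 0.7667)/178] = 0.0436. Power for non-inferiority on related adverse events is Φ((0.15 − 0.0333)/0.0436 − 1.96), about 76%, against 94.3% with no imbalance. An adjusted estimate can therefore also work in Altis's favour.

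**The case against.** The strongest reply is that a large imbalance would not be hidden. SAP 12.4 tabulates and tests every listed covariate and, where a difference is significant, promises to look at the effect of the relevant factors on success rates. A 40% v 20% imbalance gives z = 0.20/√(2 × 0.30 × 0.70/178) = 4.1 and would almost always be flagged. This stands, and it rules out a stronger reading that a reader might infer: that the imbalance would be invisible, or that no adjusted look at these endpoints could ever be made. The documents do not support that.

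SAP 12.4 does not close the gap, however. It is conditional on significance, names no model and does not name these two endpoints. At 35% v 25% the same formula gives z = 2.1, so detection is roughly a coin toss. At 33% v 27% it gives z = 1.2, and the bias would usually go unflagged.

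Three further replies:
- **Scope.** Protocol 3.3.5 and 7.8 mention secondary analyses in their openings. That wording places the propensity analysis alongside those analyses. It specifies no adjusted model for them, and the SAP prevails.
- **Gating.** The secondary tests run only after primary safety succeeds, and revision only after related adverse events. The tabulated rates are therefore upper bounds on the actual false-claim rates. Primary safety does get an adjusted model, so some adjusted safety evidence will exist. Gating does not remove confounding from a different and more frequent outcome.
- **Status.** Even for the primary endpoints, the crude test decides and the propensity model is supplementary. That is why the fix asks for no stricter rule on the secondary endpoints than on the primaries.

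**Conclusion.** The point holds as a gap in what is prespecified. Followed as written, the plan can yield non-inferiority and superiority claims on two powered safety endpoints, in a non-randomised cohort, with no planned estimate adjusted for the factors it lists as risk factors.

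The size depends on an imbalance that the documents do not give. Under the assumed single factor with risk ratio 2, related adverse events carry 0.9 to 2.9 points of bias, with false superiority of 4.2% to 10.6%. Revision/resurgery carries 0.2 to 1.4 points over comparator rates of 5% to 10%, with false superiority of 3.0% to 7.0%. These figures are before gating. The upper ends need a large imbalance that the baseline comparison would show. The direction could equally be against Altis.

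No stated sample size is wrong, and the primary conclusions are not affected by this point. It is a worthwhile, inexpensive improvement rather than a fault that invalidates the design.

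**What to change.** Extend SAP 12.6.3 to the endpoints in 12.7.1 and 12.7.2:

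1. Fit the same logistic model, with the propensity score already computed for each woman, to related adverse events and to revision/resurgery through 36 months in the mITT population.
2. Convert each fit by standardisation over the mITT population to an adjusted risk difference (Comparator – Altis) with a 95% confidence interval, and name the interval method (delta method or bootstrap).
3. Report it beside the crude result, against −0.15 and −0.10, as a prespecified supplementary analysis with the same status as for the primary endpoints.
4. State that a crude non-inferiority or superiority claim will be qualified in the report if the adjusted interval does not support it.

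**Cost.** A short specification for the standardisation (the planned logistic model does not by itself give a risk difference), two more model fits, and the possibility that a claim must be qualified. The crude tests keep their power: 94.3% for related adverse events, and 88.2% for revision at a 10% rate. The adjusted interval may be wider. If adjustment inflated the variance by an assumed factor of 1.1 to 2.0, the chance that the adjusted interval also clears the margin when the arms are truly equal would be 92.1% to 70.6% for related adverse events and 85.0% to 60.4% for revision. This is a reason to keep the adjusted result supplementary. No sample size changes.
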